#### **4.1.2 Theoretical Framework**

The theoretical framework for this study is the NASSS framework [4]. Although originally developed in order to explain variation in the adoption of technology in healthcare settings, this framework has wider application arising from its focus on providing explanations for the non-adoption, abandonment or failure to scale-up, spread and sustain innovation in the long-term. The NASSS framework identifies 7 key explanatory factors related to: the condition/illness (in this case end-stage renal disease); the technology (in this case home therapies); the value proposition (to both the patient and the provider); adopters (staff, patients and carers; and their role, identity and input required); organisation (including capacity, capability and readiness to change); the wider system (including policy context, legal issues, socio-cultural context) and embedding and adapting over time. Each factor is considered in relation to complexity theory, prompting an analysis of whether it is simple, complicated or complex [4]. The framework is designed to generate rich descriptions and explanations of the implementation of innovation in real-world settings.

Although home therapies (PD and HHD) have been used to treat end-stage renal disease for many years, uptake rates have remained stubbornly low in England and have failed to be adopted widely despite evidence in favour of positive clinical and patient outcomes and multiple technological developments improving reliability, acceptability and cost within the two home dialysis modalities. The NASSS framework will therefore help to provide a theoretical framework to explain and illuminate how and why some renal units have been able to exceed national average uptake rates.

For the initial stage of intervention development, the study draws on the COM-B framework for designing behaviour change interventions.[5] This framework is now internationally recognised as one of the most robust evidence-based frameworks for behaviour change, and is highly relevant to home therapy uptake, which, as a home-based rather than hospital-based therapy, requires new or different behaviours from patients, carers/family and staff.

## **5 STUDY SETTING (by Work Package)**

**5:WP1** Four case study sites selected from the 52 dialysis units in England. Selection of the four case study renal units involved two-stage purposive sampling and was undertaken prior to grant submission. Stage 1 involved assigning each renal unit in England that offers PD and/or home haemodialysis as treatment options for renal patients (n=52) to one of four categories based on a home therapies uptake taxonomy developed using UK Renal Registry data [43]. The four categories in the taxonomy are: i) high uptake of home therapies (top 15% nationally based on the proportion of renal patients at each unit treated using home therapies); ii) high uptake of home therapies amongst BME patients (top 15%); iii) renal units with home therapy uptake for all patients at rates around the national median (ten above the median and ten below); and iv) renal units with home therapy uptake for BME patients at rates around the national median (ten above the median and ten below). As it is important that case study sites have a large enough cohort of patients potentially eligible for participation in the ethnography, renal units with fewer than 50 total renal patients and/or fewer than 20 BME patients were excluded from consideration as part of the Stage 1 sampling process.

Sampling in Stage 1 produced a long-list of potentially eligible renal units within each of the four groups in the taxonomy. Stage 2 involved further sampling to select a single case study site from each group, ensuring a balanced selection based on: maximum geographical variation across England (North, Midlands, South, London); population density of a renal unit's catchment area (urban/rural); sociodemographic characteristics of a unit's patient population (less affluent/affluent/mixed); and ethnic diversity (high/low BME populations). In addition to these criteria, a flexible approach was used in selecting the four case study sites that balanced the need for maximum variation in unit characteristics and practice with practicalities such as sites' willingness to participate in the study and accounting for the potential influence of unit transplantation rate on home therapy uptake. As transplantation may have an impact on home therapy rates, both units that are or are not also transplant centres will be represented.

**5:WP2:** The survey will be sent to all 52 of the Dialysis Units in England. The survey data will be linked with the patient level routine data returns made from the 52 units to the UK Renal Registry. Linkage will be undertaken at Keele University.

**5:WP3:** Is all data driven. Research data will be obtained through Keele University and the UK Renal Registry under a data-sharing agreement.

**5:WP4:** The data synthesis, using aggregated data, will be undertaken by the research team in workshops held on University premises.

**5:WP5:** The intervention development will be co-designed with an Independent Reference group comprising patients, carers, health professionals and members of the national dialysis reference group. These workshops will be held on University Premises.

***In the following sections the protocol is ordered by WORK PACKAGE. Each paragraph is numbered first by the WP identifier, e.g. WP1: detail on rationale and design where needed, followed by the main section number and the appropriate subsection where relevant in the following order:***

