### **WP1:8.3 Data synthesis and analysis**

Observational data, ethnographers' field notes and interview transcripts will be imported into the qualitative data-analysis software QSR NVivo 12 for inductive thematic analysis [61]. Each site's data will be analysed separately to capture distinctive centre effects. Two researchers will generate an initial coding framework and fields using a broadly representative sample of 10% of each type of data. Results will be reviewed by the team and adjusted to produce a codebook and coding framework. The analytical approach will be inductive, based on iterative data coding and comparison.

Analysis will be guided by the aim of identifying the specific approaches of units and understanding how different approaches are perceived and acted on by patients. Where data do not fit with existing themes, new themes will be developed or existing ones revised until all the data can be assigned to themes. Data from staff and patients will initially be analysed separately. Data from patients, carers and staff will be combined with the documentary analysis to build up a detailed picture of each site. Themes will then be mapped to the NASSS framework in order to identify the main factors which influence the uptake of home therapies, and how these factors interact. A second stage of analysis will look across the four sites' ethnographies to characterise the centre effect and identify promising practices that can be explored in the subsequent national survey.

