#### **WP2:8.7 Subject population**

All English renal units and all patients commencing renal replacement therapy in them.

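### Four units chosen on uptake help nominate the practices to be studied and then sit inside the 52-unit model that ranks them, which favours uncommon practices shared by the exemplar sites

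*Protocol*

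**What the plan says.** Under Study Setting, the WP1 entry reads "Four case study sites selected from the 52 dialysis units in England". It defines four categories by uptake. The first is "high uptake of home therapies (top 15% nationally based on the proportion of renal patients at each unit treated using home therapies"; the second applies the same 15% cut to BME patients only; the other two are bands of ten units above and ten below the median, one for all patients and one for BME patients. Then "Stage 2 involved further sampling to select a single case study site from each group". The Registry report cited for this taxonomy (reference 43) has data to the end of 2017.

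WP1:8.3 looks across the four sites to "identify promising practices that can be explored in the subsequent national survey". The WP2 Survey Design section turns WP1 findings, with the literature, into survey questions. WP2:8.3.2 lets the literature review and the ethnography inform which variables enter the graphical Markov model and in what order.

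The quantitative phase covers every unit: "The survey will be sent to all 52 of the Dialysis Units in England", and the answers are "linked with the patient level routine data returns made from the 52 units to the UK Renal Registry". WP2:8.7 gives the population as "All English renal units and all patients commencing renal replacement therapy in them". Section 4.1.1 says the factors will be evaluated in the exemplar case-study sites as well as in average performers. WP2:8.3.2 presents the model as a robust basis for choosing intervention factors, and WP5:7.1 takes 6–10 factors into the first workshop.

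**The concern.** The same four units help generate the hypotheses and contribute to the estimates that rank them. Because they were picked on the outcome, a practice noticed at a high-uptake site and not at a near-median site already has an observed association with uptake in those units. Carrying them into the model counts that association a second time.

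The 27,000 patients do not dilute this. WP2:8.1 says the sample size is the number of centres, and a unit practice varies only between centres. At stake is the factor list: a practice that does nothing could be ranked above one that works. The uncommon, promising practices that WP1 looks for are the most exposed.

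The protocol keeps generation and evaluation apart elsewhere. Survey pilot staff are not invited to the main survey (WP2:7), and Reference Group members must have had no direct part in WP1 (WP5:7).

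**Working it through.** The protocol gives no alpha, effect size or power for this analysis, so there is no planned figure to reproduce.

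**Shares.** Case-study units: 4/52 = 7.7% of centres. Top-15% group: 0.15 × 52 = 7.8, about 8 units.

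**Null simulation.** There were 40,000 runs per setting.
- From the protocol: 52 units; exemplars drawn from the top 8; near-median sites drawn from the 20 units around the median.
- Assumed: a binary practice unrelated to uptake, present in one or two exemplar sites and absent in the remaining case-study sites, which are drawn from the near-median band; prevalence 15%, 30% or 50% in the other 48 units; correlation 1.0, 0.8 or 0.5 between uptake at selection and at analysis.
- Comparison: two-sample t-test of centre uptake (in SD units), two-sided 5%, hence 2.5% in the favourable direction.

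All 52 units, spurious mean difference in SD / favourable-direction error:

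| Exemplars with practice | Prevalence elsewhere | Correlation 1.0 | 0.8 | 0.5 |
|---|---|---|---|---|
| 1 | 15% | 0.207 / 6.8% | 0.169 / 5.6% | 0.102 / 4.2% |
| 1 | 30% | 0.103 / 5.0% | 0.080 / 4.3% | 0.050 / 3.6% |
| 1 | 50% | 0.059 / 3.6% | 0.045 / 3.3% | 0.029 / 3.0% |
| 2 | 15% | 0.368 / 14.3% | 0.294 / 11.0% | 0.183 / 6.4% |
| 2 | 30% | 0.196 / 8.5% | 0.157 / 6.7% | 0.095 / 4.8% |
| 2 | 50% | 0.116 / 5.6% | 0.095 / 4.9% | 0.062 / 3.9% |

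Total two-sided error over the same grid is 4.8–14.3%. In the 48 units outside WP1, the mean difference is −0.003 to 0.004 SD, favourable-direction error 2.4–2.6% and two-sided error 4.8–5.1%.

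**Rarer practices.** With both exemplars in the top 8 overall, uptake unchanged and a perfect split between high and near-median sites, two-sided error is 19%, 12% and 8% at 10%, 20% and 30% prevalence. If the second exemplar is instead chosen on BME uptake (correlation with overall uptake assumed 0.6–0.7) and uptake has drifted (correlation 0.5–0.8), it is about 5–11%.

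**Precision cost of the 48-unit fit.** SE is proportional to √(1/users + 1/non-users), using expected counts. Two of the four excluded sites are users and two are not.
- 10%: 52 units, 6.8 and 45.2, sum 0.1692; 48 units, 4.8 and 43.2, sum 0.2315; √(0.2315/0.1692) = 1.17.
- 20%: 11.6 and 40.4, sum 0.1110; 9.6 and 38.4, sum 0.1302; ratio 1.08.
- 30%: 16.4 and 35.6, sum 0.0891; 14.4 and 33.6, sum 0.0992; ratio 1.055.

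**The case against.** Surveying every unit is not an error. WP2 is described as a whole-country study, the design is labelled exploratory, and Section 4.1.1 evaluates the case-study sites on purpose. A leave-out sensitivity analysis could also sit in a statistical analysis plan that is not shown. This stands as a reason to keep all 52 units in the main analysis. It does not remove the point, because the protocol itself fixes the population as every unit and gives the result a selecting role.

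No section says that items are nominated by contrasting high with median sites. Each site is analysed separately, themes are mapped to the NASSS framework, and the literature also supplies items. The nomination pattern simulated above is therefore an assumption, and literature-derived variables are unaffected. The t-test also stands in for adjusted sequences of regressions, for which the protocol states no significance rule, and the workshops in WP4 and WP5 can challenge any factor.

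Three stronger readings are tempting but not supported:
- A reader might take 19% as the expected error. It is an upper bound: Section 5 makes one exemplar high on BME uptake only, and the selection data end in 2017.
- A reader might infer that nine months of fieldwork alters these units' survey answers. That is possible, but nothing in the protocol shows it, and uptake itself comes from the Registry.
- A reader might price the 48-unit fit at √(52/48), about 4%. That ignores the loss of two users of a rare practice.

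**Conclusion.** The overlap is plain in the text, and its direction is favourable to practices nominated at the exemplar sites. Its size depends on assumptions that the protocol cannot settle: how many exemplars share the practice, how common it is elsewhere and how far uptake has moved since selection. The middle case (30% prevalence, correlation 0.8) gives 4.3% favourable-direction error with one exemplar and 6.7% with two, against 2.5%. The worst case in the grid is 14.3%. The two-exemplar rows treat both sites as high on overall uptake and so are an upper bound. The one-exemplar rows place the other three sites near the median; if the second exemplar were a high-uptake unit without the practice, the bias would be smaller.

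This calls for an added analysis. It does not invalidate the 52-unit model.

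**What to change.** Add to WP2:8.3.2 that, for practices nominated by WP1, effects are also estimated in the 48 units that were not case-study sites and are reported beside the 52-unit estimates. Record which survey items came from WP1 and which from the literature, so that the set is fixed before linkage. State in WP4 that both estimates are weighed when the 6–10 factors are chosen. Keep all 52 units for the main and descriptive analyses.

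Do not require agreement in direction and size as a condition for listing a factor. At 10% prevalence the 48 units contain about five users, so such a rule would turn largely on noise, could discard a real innovation and would override the mixed-methods synthesis.

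The cost is a refit of the relevant regressions on data already held. Standard errors in that fit are larger by about 5% at 30% prevalence, 8% at 20% and 17% at 10%.

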6 ELIGIBILITY CRITERIA

7 STUDY PROCEDURES

8 STATISTICS AND DATA ANALYSIS

9 DATA HANDLING

## **WORK PACKAGE 1 (WP1): QUALITATIVE RESEARCH: A FOCUSED ETHNOGRAPHY**

### **WP1: RATIONALE**

Qualitative research methods, underpinned by an ethnographic approach, are best suited to identify the main factors that facilitate or impede uptake of home therapies and to provide in-depth understanding of the interplay between factors related to health professionals, patients and carers/families, the organisation and its culture [33]. To date, there are limited ethnographic perspectives into the workings of renal units; pioneering research in renal units includes research on chronic kidney disease in paediatric settings [34,35] and on haemodialysis [36,37]. Ethnographic research is conducted in context, and the immersive *in-situ* method allows the research team to gain direct insights into the learning process about choice of treatment place (home or hospital) and treatment type, through contextual observations and interviews [38]. Ethnographic fieldwork will allow the research team to collect several qualitative data sets on different experiences in the round – each representing a particular view based on the position of that stakeholder – and these will then be analysed in accordance with the context in which they were collected [39]. The key stakeholders are those involved in the decision-making process and those who have a stake in home therapies: patients, family and carers and healthcare professionals working in renal units.

### **WP1: DESIGN**

We will use a comparative ethnographic approach – collecting observational, interview and reflective field data across four centres, each centre representing a ‘case study’ considered sufficient to generate new insights [40]. This case study approach will allow the centre effect to be explored by identifying the collective ways, distinct to each unit’s organisational culture, that staff view and undertake their work and how patients respond through their treatment choices. An ethnographic research design is sufficiently unstructured to allow for emergent new findings (e.g. inclusion of new participants whose relevance becomes apparent during the research), but systematic enough to ensure that factors contributing to centre effects in each site can be clearly identified, so that these can be used in later stages of the study [41]. ‘Focussed ethnography’ allows the ethnographers to focus on a particular aspect of a setting (here: everything that relates to home therapy) rather than on the whole socio-cultural system. Ethnographers, working in pairs in each site, will spend nine months

in four case study renal units (see section 5 for detail of case study site selection) researching how choice about treatment is proposed, negotiated and decided.

## **WP1:6 ELIGIBILITY CRITERIA**

Qualitative data will be collected among patients and healthcare professionals in the four renal units. The primary focus will be on patients who will be *starting* renal replacement therapy for the first time, as this is the largest group of patients, and where the range of treatment choices is often greatest. The semi-structured interviews may also include a small number of patients who are already receiving renal replacement therapy, but who need to switch to a new treatment, as discussions about home therapy options are also relevant to this patient group.

Ethnographic data will also be collected from renal unit staff, who will participate in semi-structured interviews to explore in depth how patients are supported to make treatment choices, their reflections on factors that help and hinder treatment choices (particularly for BME and less affluent patients), and what units have done to encourage the uptake of home dialysis amongst these groups of patients.

### ***WP1:6.1 Inclusion criteria (patients)***

- Patients expected to start renal replacement therapy with dialysis within the next 3-6 months.
- Patients with unplanned dialysis initiation, even if dialysis has already commenced in whom a decision regarding preferred dialysis modality has not been made
- Patients starting dialysis following a failed kidney transplant.
- Aged 18+
- Carers, family members or individuals supporting eligible patients

### ***WP1:6.1 Inclusion criteria (staff)***

- Renal unit staff members who have regular contact with renal patients and who engage in treatment discussions, or who have oversight of decision-making processes within the renal unit (consultants, registrars, specialist home therapy nurses, pre-dialysis nurses, dialysis unit ward staff, dietitians, psychologists/counsellors, clinical lead, business manager)

### ***WP1:6.2 Exclusion criteria (patients)***

- Unable to consent to take part, including those with significant cognitive impairment (although mild cognitive impairment will not preclude participation)
- People with acute kidney injury or anticipated to recovery of kidney function

### ***WP1:6.2 Exclusion criteria (staff)***

- Renal unit staff with who do not have regular contact with renal patients, who do not engage in treatment discussions, or who do not have oversight of decision-making processes within the renal unit

## **WP1:7 STUDY PROCEDURES**

Data will be collected over a 9 month period in each of the four case study renal units using three qualitative research methods concurrently: non-participant observation; short reflection interviews and

semi-structured individual face-to-face interviews. All of these data collection methods will include renal unit staff and patients, with carers/family members involved in reflection and semi-structured interviews only.

#### ***WP1:7.0.1 Access to case study sites and site setup***

The four participating centres are:

1. University Hospitals of Derby and Burton NHS Trust
2. Salford Royal NHS Foundation Trust
3. Portsmouth Hospital NHS Trust
4. King's College Hospital, London NHS Foundation Trust

A one-month site set-up period in each participating centre will allow researchers to consult with and engage stakeholders prior to the start of data collection, ensuring all ethical and local approvals are in place [45], and gaining familiarity with the working procedures within each centre. This co-design phase of the ethnographic fieldwork will include conversations with clinical leads, key staff members and patient representatives about how services are organised/experienced and will highlight the areas of the service they see as relevant to the Inter-CEPt study. The team of ethnographers will all have research passports with each site to allow them access to undertake the research.

#### ***WP1:7.0.2 Non-participant observation of relevant meetings in each renal unit***

The ethnographers will conduct non-participant observation [46-48] of relevant meetings in each renal unit, focussing attention mainly on dialysis choices, how options are discussed and the treatment decision-making processes. These would be 'large' meetings (i.e. not one-to-one patient-healthcare professional consultations). Examples of such meetings include patient education meetings and multi-disciplinary renal team meetings.

Data collection will focus on treatment choice, the information provided around dialysis choice, questions asked and topics discussed during meetings and which assumptions are made, by both patients and health professionals, around dialysis choice and patient characteristics (e.g, BME, socio-economic deprivation, low health literacy). Ethnographic field notes will be written up frequently and discussed weekly with the research team [49,50]. Although most data will be cross-sectional, collected from different patients at single points in time, we will take any opportunities that arise to observe the same patients in different settings/encounters, in order to add depth to their reflections about their treatment decisions.

#### ***WP1:7.0.3 Non-participant observation of dialysis choice consultation***

The ethnographers will also conduct non-participant observation [46-48] of the consultation in which the healthcare professional discusses dialysis treatment options with the patient. Data collection in this setting will focus on the content of health professional-patient interaction; the information provided to patients on treatment options and how this is relayed; assumptions made by both patients and health

professionals; and the nature of these encounters, including the tone of conversations, language used, verbal and non-verbal reactions.

